Moreover, chemotherapy and thrombosis for over three decades, it remains an underappreciated risk that has not been routinely incorporated into thrombosis risk assessment models.[42] Cytotoxic chemotherapy has a multifactorial contribution to the risk of thrombosis. It induces vascular injury through apoptosis. In the case of cisplatin, this leads to release of prothrombotic particles that trigger thrombin generation via tissue factor independent mechanisms along with drastically increased vWF activity. Other agents, like 5-FU, also drive thrombin formation in combination with depleted protein C activity. L-asparaginase administration is tied to drastically decreased protein C, protein S, and antithrombin levels, creating a prothrombotic milieu through loss of anticoagulant factors. VEGF inhibition does not directly lead to thrombosis, but instead 'primes' the endothelium through a VEGF starved state to be more susceptible to injury. Additionally, platelet activation through PAR-1 and increased Gp IIb/IIIa activity in the case of immunomodulatory agents or increased vWF among others in the case of small molecule inhibitors contributes to this 'primed' state.[43-81]

Cancer patients undergoing systemic treatment for their malignancy are among the highest risk populations for thromboembolic complications; often, the treatment itself contributes to this risk. Recognition of the antineoplastic agents most likely to cause thrombosis can help raise provider awareness and lead to earlier diagnosis and treatment.

In our approach, we will protect our patient taking under consideration their treatment (surgery either chemotherapy)

Study Objective

In this study we will collect Real World Data of our clinical practice regarding Thromboprophylaxis in high thrombotic risk solid tumors patients undergoing surgical and /or chemotherapeutical treatment, for one year following the protocol initiation date.

- **Specifically we will focus on the following :**
 - Number of thrombotic events
 - Anti-thrombotic management dosage & duration
 - Any bleedings related to anticoagulation
 - Patients' adherence and compliance

Study Design

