This is a prospective, phase IV, observational, non-interventional cohort study that aims to record the daily clinical practice regarding thromboprophylaxis in high thrombotic risk cancer patients (under surgery or chemotherapy) initiated December 2018 for a year time. Patients demographic data, cancer type and stage, anticoagulant treatment dose & duration, efficacy (VTE events), safety (bleedings) and information about adherence will be collected; more than one outcomes could be recorded.

Subject Completion/Withdrawal

Subjects may withdraw from the study at any time without prejudice to their care. They may also be discontinued from the study at the discretion of the Investigator for lack of adherence to study treatment or visit schedules, AEs, or due to termination of study observation period. The Investigator may also withdraw subjects who violate the study plan, or to protect the subject for reasons of safety or for administrative reasons. It will be documented whether or not each subject completes the clinical study. If the Investigator becomes aware of any serious, related adverse events after the subject completes or withdraws from the study, they will be recorded in the source documents and on the CRF.

Clinical Adverse Events

Clinical adverse events (AEs) will be monitored throughout the study.

Adverse Event Reporting

Since the study procedures are not greater than minimal risk, SAEs are not expected. If any unanticipated problems related to the research involving risks to subjects or others happen during the course of this study (including SAEs) these will be reported in accordance with current regulations. AEs that are not serious but that are notable and could involve risks to subjects will be summarized in narrative format.

Authorized staff will perform periodic site visits to review CRFs for completeness, but will have no direct access to patient records; although they could request further information from the hospital staff. The anonymized data will be collated centrally and entered into an electronic database using double data entry where appropriate. Any discrepancies identified by electronic logic checks and will be resolved using data clarification forms sent to sites.

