Ethics committee approval will be obtained where approval of a prospective non-interventional study is required. This study will be conducted in full accordance all applicable Research Policies and Procedures and all applicable laws and regulations. The investigators will perform the study in accordance with this protocol, will obtain consent, and will report unanticipated problems involving risks to subjects or others in accordance with Policies and Procedures and all regulatory

requirements. Collection, recording, and reporting of data will be accurate and will ensure the privacy, health, and welfare of research subjects during and after the study.

Subject Population **Inclusion Criteria**

key criteria for Inclusion and Exclusion:

1. Patients who were diagnosed with histological confirmed high thrombotic risk cancers (GI, thoracic, gynecologic and genitourinary) undergoing surgery
2. Age \geq 18 years

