Major bleeding will be defined as overt bleeding associated with: a fall in hemoglobin of 2 g/dL or more, or leading to a transfusion, or bleeding that occurs in a critical site or contributing to death.

- **Bleeding in a critical area or organ such as:**

Retroperitoneal

Intracranial

Intraocular

Intraspinal

Intra-articular

Pericardial

Intramuscular with compartment syndrome

- **A clinically overt bleeding event**
 - that is associated with a fall in hemoglobin of 2.0 g/dL (>1.24 mMol/L) or more, or
 - leading to a transfusion of ≥ 2 units of packed red blood cells or whole blood.
- **Bleeding contributing to death**

Other clinically relevant non-major bleeding will be defined as overt bleeding not meeting the criteria for major bleeding but associated with medical intervention, unscheduled contact (visit or telephone call) with a physician, (temporary) cessation of study treatment, or associated with discomfort for the patient such as pain, or impairment of activities of daily life. All other bleeding events will be classified as minor

Statistical And Analytic Plan	
Descriptional statistical analysis will be performed for all study data along with epidemiology methods. Continuing parameters will be presented with standards descriptional statistical measures (mean values, median values, percentages etc.) and the results will be presented accordingly into tables. For more complex correlations we will use, among other methods, chi-square tests, ANOVA and t-tests, in order to evaluate the relationships between different patient and disease characteristics, such as:
 
 • Number of patients enrolled • Tumor characteristics • Co-morbidities • Type of Surgical operation • Type of antineoplastic treatment • Type of thromboprophylaxis therapy • Therapy outcomes • Number of therapy disruptions for any reason • Complications (AE- SAE) 
and to present them, accordingly. Due to the fact that this is an observational study the results of all correlations will be carefully discussed and will be used only to assess hypotheses.

REFERENCES	References

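### Surgery and chemotherapy patients form one cohort, but the analysis plan sets no group, denominator or stratum by treatment setting

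*Combined protocol and SAP*

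**What the plan says.** The Study Objective covers "high thrombotic risk solid tumors patients undergoing surgical and /or chemotherapeutical treatment". The Study Design describes one cohort of "high thrombotic risk cancer patients (under surgery or chemotherapy) initiated December 2018 for a year time". The background treats the two settings separately, and the chemotherapy introduction ends by saying that "we will protect our patient taking under consideration their treatment (surgery either chemotherapy").

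Inclusion criterion 1 and its mirror exclusion criterion, however, name only patients with "high thrombotic risk cancers (GI, thoracic, gynecologic and genitourinary) undergoing surgery". Read literally, they admit no one who is treated with chemotherapy alone.

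Observation has no fixed length. Under Study Phases it runs over the treatment period. Under Study Duration it ends, where applicable, with a visit four weeks after hospital discharge.

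The Statistical And Analytic Plan states: "Descriptional statistical analysis will be performed for all study data along with epidemiology methods". For relationships it names "chi-square tests, ANOVA and t-tests, in order to evaluate the relationships between different patient and disease characteristics", and it leaves room for other methods. The listed characteristics include type of operation, type of antineoplastic treatment, type of thromboprophylaxis, therapy outcomes and complications. No analysis group, denominator, stratum or adjustment is tied to setting. Correlations are to be discussed with care and used only to assess hypotheses.

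**The concern.** The study exists to report four things: thrombotic events, dosage and duration, bleeding, and adherence. If setting affects any of them, one figure for the whole cohort is a weighted average whose weights are whatever mix of patients was enrolled in the year. Another centre could not apply it to its own surgical or chemotherapy patients. Observation time that follows treatment adds to this, because a longer course leaves more time for an event to be recorded.

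The comparisons carry a second risk. Prophylaxis type and therapy outcomes are both on the list to be related. If one type is used more in the setting with the higher risk or longer observation, an unadjusted test attributes to the prophylaxis a difference that belongs to the setting.

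**Working it through.** The plan gives no sample size, significance level or expected rate, so there is no figure of its own to reproduce. What follows illustrates the mechanism.

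**Inputs from the documents.** VTE rates quoted for surgery: 2.6% and 5.6% (meta-analysis, extended versus standard prophylaxis) and 4.8% and 12% (randomised trial of extended prophylaxis). Surgical course: up to 4 weeks when extended, 7–10 days or at least 10 days otherwise (guideline table).

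**Assumptions.** VTE rate and course length under chemotherapy, split of prophylaxis types between settings, patient numbers, and a two-sided 5% level. The documents give no absolute VTE rate, risk window or course for chemotherapy.

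**1. Pooled event rate.** Pooled rate = w × p1 + (1 − w) × p2, where w is the share of the cohort in the lower-risk setting.
- p1 = 2.6%, p2 = 12%: w = 0.8 gives 4.5%, w = 0.5 gives 7.3%, w = 0.2 gives 10.1%.
- p1 = 2.6%, p2 = 5.6%: 3.2%, 4.1% and 5.0%.

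**2. Pooled mean duration.** Mean = w × s + (1 − w) × c, with w now the surgical share, s the surgical course and c the chemotherapy course.
- s = 28 days, c = 90 days: w = 0.7 gives 0.7 × 28 + 0.3 × 90 = 47 days; w = 0.3 gives 71 days.
- s = 28 days, c = 180 days: 74 and 134 days.
- The shift as w goes from 0.7 to 0.3 is 0.4 × (c − s): 25 or 61 days with s = 28, and 32 or 68 days with s = 10.

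**3. Comparison by prophylaxis type, with no true effect of type.** Let 80% of type A be used in surgery and 80% of type B in chemotherapy, with equal numbers of each type. Expected risks are A = 0.8 × pS + 0.2 × pC and B = 0.2 × pS + 0.8 × pC. For pS = 2.6% and pC = 8%, A = 3.68%, B = 6.92%, and the ratio B/A is 1.88. Simulated rejection rates of the pooled chi-square test:

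| pS | pC (assumed) | Use | Ratio B/A | 200 per type | 400 per type |
|---|---|---|---|---|---|
| 2.6% | 8% | 80/20 | 1.88 | 29–30% | 53% |
| 2.6% | 5% | 80/20 | 1.47 | 11% | 18% |
| 5.6% | 8% | 80/20 | 1.24 | 8% | 13% |
| 4.8% | 5% | 80/20 | 1.02 | 5% | 5% |
| 12% | 8% | 80/20 | 0.79 | 12% | 20% |
| 2.6% | 8% | 60/40 | 1.23 | 7% | 10% |
| 2.6% | 8% | 50/50 | 1.00 | 5% | 5% |

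A Cochran-Mantel-Haenszel test stratified by setting rejects about 5% of the time in every row.

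A wider grid used the quoted surgical rates as setting-specific rates, 200 to 1,000 patients in total, half in each setting. Where both risk and use differed by setting (70/30 or 80/20 use), the pooled test rejected 5.9% to 94.1% of the time and the stratified test 4.6% to 5.3%. Where either was equal across settings, the pooled test rejected 4.1% to 5.2%.

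**The case against.** The strongest reply is that the plan never says the settings will only be pooled. Its phrase about all study data may simply mean every variable collected. Operation type and antineoplastic treatment are listed for presentation, and the choice of methods is left open. That stands in part: pooling is inferred from the absence of any split. What can be said is that separation is not planned.

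A reader might also infer that setting determines the agent, the course length and the VTE risk. The documents do not show this. They say only that treatment is taken into account, they favour low-molecular-weight heparin in both settings, and they describe surgical risk as staying high for 4 to 12 months. Nor do they support a prediction that one prophylaxis type will look worse. The 30% and 53% figures start from 2.6%, the lowest surgical rate quoted; 5.6% brings them down to 8% and 13%, and 12% reverses the direction.

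It would also be wrong to say that the listed items cannot separate the settings. Whether an operation and an antineoplastic treatment are recorded is what identifies them.

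Finally, the study is exploratory and the plan says so. That weakens the false-positive argument. It does not reach the descriptive event and duration figures, because the caveat is attached to the correlations alone.

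**Conclusion.** The point holds as a gap in the analysis plan that should be closed. Followed as written, the plan gives pooled VTE, bleeding and duration figures that move with case mix wherever the settings differ, and it allows comparisons by prophylaxis type that can be confounded by setting. Confounding requires prophylaxis type to differ by setting together with risk or observation time; without both there is no inflation.

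Size and direction cannot be taken from the documents. Under the assumed inputs the pooled false-positive rate runs from about 5% to 30% or more, against about 5% when stratified. These figures rest on assumed chemotherapy rates, prophylaxis mixes and patient numbers, and they illustrate the mechanism only.

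The eligibility conflict comes first, because it decides which groups exist. If only surgical patients are eligible, the contrast becomes surgery alone versus surgery plus chemotherapy, and the need to separate remains. The study is descriptive and exploratory, so this is worth fixing but does not invalidate it.

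**What to change.** 1. Reconcile the surgery-only wording of inclusion and exclusion criterion 1 with the Study Objective and Study Design.
2. In the Statistical And Analytic Plan, use the recorded operation type and antineoplastic treatment to define three groups: surgery only, chemotherapy only (if eligible), and both. State a date-based rule for assigning patients and events in the group with both treatments.
3. Report all four objective items within each group, with its own denominator and observation time. Show the pooled total as a secondary line.
4. Replace the unadjusted test of outcome by prophylaxis type with one stratified by setting (for example Cochran-Mantel-Haenszel) or a regression adjusted for setting, and keep it exploratory.

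The cost is plan wording and extra table columns. Steps 2 and 3 need treatment and event dates; the case report form is not among the text available, so whether it already captures them should be checked. The statistical price is smaller denominators and wider intervals within each group.

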Surgical setting	Incidence of DVT, %	Incidence of PE, %
Major abdominal and pelvic surgery (colorectal/gynecological)	15–40 ^a	1.3–2 ^d
Major open urological surgery	15–40 ^a	0.2 ^e
Neurosurgery	15–40 ^a	Insufficient data
Thoracic surgery	4–14 ^a	5–12 ^f
Breast surgery	0.8–2.1 ^b	Insufficient data
Laparoscopic surgery	1–11 ^c	Insufficient data

Abbreviations: DVT, deep vein thrombosis; PE, pulmonary embolism.

Source: Adapted and modified from Geerts et al.¹⁶

^aRoutine screening of asymptomatic patients without prophylaxis.

^bSymptomatic patients without prophylaxis or mechanical prophylaxis alone (from retrospective studies).

^cRoutine screening of asymptomatic patients with or without prophylaxis.

^dSymptomatic patients without prophylaxis.

^eSymptomatic patients without prophylaxis or mechanical prophylaxis alone.

^fRoutine screening of asymptomatic patients with CT chest.

Pharmacological Prophylaxis

Pharmacological Prophylaxis for cancer patients undergoing surgery

Studies in the late 1980s and early 1990s showed that pharmacological prophylaxis reduces the risk of postoperative VTE by 60% compared with no prophylaxis.[14-17]

LMWH is generally the preferred choice of anticoagulant over UFH based on its ease of administration (once daily vs. twice to three times per day for UFH) and lower risk of heparin-induced thrombocytopenia (HIT).

Cancer patients may also tolerate higher doses of LMWH without increasing the bleeding risk further.[18]

The optimal duration of thromboprophylaxis after cancer surgery has not been established and the available data are limited to major abdominal and pelvic surgery. Although studies have shown that a longer duration of prophylaxis up to 1 month after major abdominal and pelvic surgery can further reduce the risk of VTE compared with standard duration (typically while in hospital or up to 7–10 days) [19-21]

In the ENOXACAN II trial, patients who received extended thromboprophylaxis (ETP) with LMWH up to 30 days after open surgery for abdominal and pelvic cancer had a 60% VTE risk reduction (95% CI: 10–82%), compared with those who received standard duration of 6 to 10 days (4.8 vs. 12%; $p = 0.02$).[19]

These findings are supported by a recent meta-analysis of seven RCTs and prospective studies which concluded that ETP is associated with a significant risk reduction of all VTE (2.6 vs. 5.6%; (RR: 0.44, 95% CI:

[figure not shown]
0.28–0.70) and proximal DVT (1.4 vs. 2.8%; RR: 0.46, 95% CI: 0.23–0.91). [22]

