IVC filter	ACCP 2012	
 IVC filter should not be used for primary VTE prevention for all risk groups
	ASCO 2015	
 Not specified in primary prophylaxis setting
	ESMO 2011	
 Not specified in primary prophylaxis setting
Duration of thromboprophylaxis	ACCP 2012	
 Not specified
	ASCO 2015	
 7–10 d
	ESMO 2011	
 At least 10 d
Extended thromboprophylaxis	ACCP 2011	
 For high-risk patients undergoing abdominal or pelvic surgery for cancer who are not otherwise at high risk for major bleeding complications, extended duration pharmacologic prophylaxis (4 wk) with LMWH is recommended over limited-duration prophylaxis
	ASCO 2015	
 Extended prophylaxis with LMWH for up to 4 wk postoperatively should be considered for patients undergoing major abdominal or pelvic surgery for cancer who have high-risk features such as restricted mobility, obesity, history of VTE, or with additional risk factors
	ESMO 2011	
 Cancer patients undergoing elective major abdominal or pelvic surgery should receive in-hospital and postdischarge prophylaxis with LMWH for up to 1 mo after surgery

Abbreviations: IVC filter, inferior vena cava filter; LDUH, low-dose unfractionated heparin; LMWH, low-molecular-weight heparin; UFH, unfractionated heparin; VTE, venous thromboembolism.

Introduction for cancer patients undergoing chemotherapy

Venous Thromboembolism (VTE) is a frequent malignancy complication which often results in serious health deterioration and death. The risk of deep vein thrombosis (DVT) and pulmonary embolism (PE) is considerably higher in cancer patients, compared to general population four to seven times [23, 24]. Venous thromboembolism is the second leading cause of death in patients with cancer and overall mortality is increased among patients who have both conditions. [25, 26, 27]

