3. ECOG >2
4. Life expectancy <6 months
5. Not signed informed consent

Study Duration	Each subject's participation will last from inclusion (enrolment visit) to follow up visit (if applicable; four weeks post hospital discharge) The entire study is expected to last by the end of 2019
Study Phases	(1) Screening : screening for eligibility, obtaining consent and administer thromboprophylaxis
Screening	
Study Treatment	(2) Observation Period : monitoring subjects over treatment time
Treatment	(3) Follow-up Phase (only if applicable e.g. by the end of treatment period)
Follow-Up	
Efficacy Evaluations	
 • Symptomatic/Suspected vein thromboembolism, including pulmonary embolism and deep vein thrombosis 
Confirmation of symptomatic PE requires symptoms of PE and one of the following findings
 
 1. A (new) intraluminal filling defect in (sub) segmental or more proximal branches on spiral CT scan; 2. A (new) intraluminal filling defect or an extension of an existing defect or a new sudden cut-off of vessels on the pulmonary angiogram;

3. A (new) considerable perfusion defect (~ 75% of a segment) with a local normal ventilation result (high-probability) on ventilation/perfusion lung scintigraphy (V/Q scan);
4. An inconclusive lung scan accompanied by documentation of (new) DVT in the lower extremities e.g., by compression ultrasound or venography.
 - Confirmation of symptomatic DVT requires symptoms of DVT and:
 - 1. A (new) noncompressible venous segment on ultrasonography
 - Incidental PE with one of the following:
 1. A (new) intra-luminal filling defect on CT scan, MRI scan, or pulmonary angiogram;
 - An inconclusive lung scan accompanied by documentation of (new) DVT in the lower extremities e.g., by compression ultrasound or venography.
 - Fatal PE is:
 1. PE based on objective diagnostic testing or autopsy or
 2. death not attributed to a documented cause and for which DVT/PE cannot be ruled out
 - Incidental DVT with the following finding:

Confirmation of recurrent incidental DVT requires inconclusive or no-symptoms of DVT and:

1. A (new) noncompressible venous segment on ultrasonography

Safety Evaluations Major, clinically relevant non-major bleeding, and minor bleeding

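### VTE and bleeding percentages can mix unequal observation times: observation length may differ by patient, and no method named in the plan accounts for it

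*Combined protocol and SAP*

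**What the plan says.** The Study Objective lists the number of thrombotic events, bleeding related to anticoagulation, and the dose and duration of prophylaxis. The Statistical And Analytic Plan offers means, medians and percentages, and then: "we will use, among other methods, chi-square tests, ANOVA and t-tests, in order to evaluate the relationships between different patient and disease characteristics". Type of thromboprophylaxis and therapy outcomes are among the items listed. The same paragraph mentions epidemiological methods without naming one, and restricts the correlations to assessing hypotheses.

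Four statements bear on how long a patient is observed:

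- Study Duration: participation runs from enrolment to the "follow up visit (if applicable; four weeks post hospital discharge").
- Study Phases, observation period: "monitoring subjects over treatment time".
- Study Phases, follow-up: "only if applicable e.g. by the end of treatment period".
- Subject Completion/Withdrawal: the investigator may discontinue a patient "for lack of adherence to study treatment or visit schedules, AEs, or due to termination of study observation period".

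No time origin, fixed event window, person-time denominator, censoring rule or rule for deaths is given for VTE or bleeding.

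**The concern.** A percentage of patients with VTE has a clear meaning only if everyone was watched for the same time, or if the analysis allows for differences. Here the window may depend on the treatment course, on length of stay, on whether the visit applies, and on early discontinuation.

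The sharpest form arises if treatment time is read as time on prophylaxis. The window is then tied to the exposure. The background describes a "standard duration (typically while in hospital or up to 7–10 days"), and the guideline table says "Extended prophylaxis with LMWH for up to 4 wk postoperatively should be considered". A short-course patient last seen when prophylaxis stops cannot contribute a later event, while a long-course patient can.

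At stake are the main descriptive results, the VTE and bleeding percentages, and any contrast between prophylaxis groups drawn from them.

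**Working it through.** The plan states no sample size, power or expected event rate, so there is no design figure to reproduce. What follows shows size and direction under stated assumptions.

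**Inputs**
- Risks of 2.6% and 5.6%, from the meta-analysis in Pharmacological Prophylaxis: "ETP is associated with a significant risk reduction of all VTE (2.6 vs. 5.6"%). That text does not call them 28-day risks; treating them so is an assumption.
- Short course ends at day 7–10; the longer course runs to 4 weeks (day 28).
- Assumed: constant hazard, 100–200 patients per group, and a share q of short-course patients last seen when prophylaxis stops. Everyone else is seen to day 28.

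**1. No true difference, groups by planned regimen**

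With 28-day risk r, the daily hazard is h = −ln(1 − r)/28, and the risk by day d is R(d) = 1 − exp(−h·d).
- r = 2.6%: R(7) = 0.66%, R(10) = 0.94%.
- r = 5.6%: R(7) = 1.43%, R(10) = 2.04%.

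The short group's observed percentage is (1 − q)·r + q·R(d), and the long group's is r. Example: r = 5.6%, d = 10, q = 50% gives 0.5 × 5.6 + 0.5 × 2.04 = 3.82%, so the ratio is 5.6/3.82 = 1.47.

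| q | r = 2.6%, day 7 / 10 | r = 5.6%, day 7 / 10 | Chi-square rejects (nominal 5%) |
|---|---|---|---|
| 25% | 1.23 / 1.19 | 1.23 / 1.19 | 5–7% |
| 50% | 1.60 / 1.47 | 1.59 / 1.47 | 6–17% |
| 100% | 3.96 / 2.78 | 3.91 / 2.75 | 11–65% |

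Rejection rates are from exact enumeration of the uncorrected two-proportion test, 100 and 200 per group.

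**2. True benefit of 2.6% vs 5.6% (ratio 0.46)**

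With the short group accruing its 5.6% evenly:
- q = 25%: 2.6/4.71 to 2.6/4.56 = 0.55–0.57.
- q = 50%: 2.6/3.82 to 2.6/3.52 = 0.68–0.74.
- q = 100%: 2.6/2.04 to 2.6/1.43 = 1.28–1.82.

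Of the shares shown, only q = 100% reverses the sign.

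**3. Groups by duration actually received**

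Assume no true difference, that a VTE ends prophylaxis, that the short course ends at day 10 with all short-course patients last seen then, and that a share s was planned short. All events to day 10 then fall in the short group. With p = R(10), the short percentage is p/[s + (1 − s)p] and the long percentage is (r − p)/(1 − p).

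For r = 5.6% the long group shows 3.64%. The short group shows 6.48%, 3.99% or 2.89% for s = 30%, 50% or 70%. The ratios are 0.56, 0.91 and 1.26 (0.55, 0.91 and 1.26 for r = 2.6%).

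**4. All surgical patients attend the four-week visit**

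Only length of stay then changes the window. For 5 against 6 weeks, R(42)/R(35) = 3.87/3.24 = 1.20 (r = 2.6%) or 8.28/6.95 = 1.19 (r = 5.6%); the test rejects in 5–8%.

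**5. The repair under the same model**

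Simulation used 200 per group, q = 50%, last contact at day 10, losses unrelated to risk and no competing deaths.
- No true difference: the day-28 ratio is 1.00 and log-rank rejects in 5% (crude chi-square 8–13%).
- True ratio 0.46: the day-28 ratio is 0.46 (crude 0.68).

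Precision for the short group at r = 5.6%: with complete follow-up, SE = √(0.056 × 0.944/200) = 1.6 percentage points. With half censored at day 10, about 98 remain and the later conditional risk is 3.64%. SE ≈ 0.944 × √[0.0204/(0.9796 × 200) + 0.0364/(0.9636 × 98)] = 2.1 points.

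**The case against.** The plan does not confine itself to crude tests: it leaves room for other methods and for epidemiological ones. That is correct, and a reader should not infer that adjusted or time-based analysis is excluded. But an unnamed method settles nothing in advance.

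Nor is it right that the protocol has no time base at all. Study Duration gives a nominal end four weeks after discharge, and the follow-up phase may mean that patients continue to be seen after treatment ends. Eligibility as written is surgical, so such a visit would naturally apply. If it does for everyone, the bias is small (step 4). The documents leave this open because both statements are conditional.

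A comparison of short against long prophylaxis is not laid down. The list names type of thromboprophylaxis, not duration, and specifies no pairs. The comparison is a reasonable inference from the listed items and the objective, no more.

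The inputs are also soft. The share q and the group sizes have no source in the documents. The constant hazard does not match the background, where 40% of symptomatic VTE in one cancer-surgery cohort came more than three weeks after surgery. Finally, limiting results to hypotheses moderates the claims that can be made, but does not make unequal windows comparable.

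**Conclusion.** The point holds in this form: observation length may differ by patient, the named methods ignore it, and crude VTE and bleeding percentages can therefore mislead. With no true difference and groups by planned regimen, the distortion is a ratio of about 1.2, 1.5–1.6 or 2.8–4.0 for 25%, 50% or 100% of short-course patients last seen at day 7–10. These figures rest on the constant hazard and on reading 2.6–5.6% as 28-day risks; they are not forecasts.

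Two stronger readings are tempting. One is that a longer regimen must show more events. Step 3 shows that the direction depends on how groups are formed, and the plan does not say. The other is that a true benefit would appear as harm. Among the shares examined, that occurs only when every short-course patient is last seen at the end of prophylaxis, which the documents do not state. The matter merits correction in a descriptive study; it does not invalidate it.

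**What to change.** 1. Reconcile the statements in Study Duration and Study Phases on when observation ends.
2. Set time zero (surgery, or first chemotherapy if such patients are enrolled) and one fixed horizon that does not depend on prophylaxis duration. Day 28 after surgery is an example, which the four-week post-discharge visit would cover. Report first VTE and first bleed as cumulative incidence with 95% CI, censored at last contact, with death as a competing event, separately by setting. Show the numbers still observed at the horizon and the reasons for earlier loss, because loss for adverse events or non-adherence may be related to risk and censoring does not cure that.
3. For any comparison of prophylaxis types, group by the regimen prescribed at time zero and use the cumulative incidence in place of chi-square on crude percentages. Label results unadjusted and descriptive when events are too few to stratify by operation type. If no one in a group is observed to the horizon, state that no comparison can be made there.

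The cost is plan wording and modest programming. Dates of time zero, event, death and last contact, and the regimen prescribed at start, must be captured; the case report form is not shown, so this needs checking. If the visit was meant as optional, either accept the censoring or add one contact for patients not otherwise seen. Intervals widen somewhat, as in the step 5 example (SE 1.6 to 2.1 points). The mismatch between surgical eligibility and the chemotherapy objective is best raised as a separate point.
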